2. PURPOSE OF THE STUDY

Acute cholecystitis is a gallbladder pathology that can lead to serious complications, and Tokyo 2013 and 2018 acute cholecystitis and acute cholangitis diagnosis and treatment guidelines have been published in order to be applied in the diagnosis phase. In these guidelines, patients were divided into three groups based on clinical findings, laboratory findings, and imaging findings, and these groups were named as Grade I, Grade II, and Grade III. While early cholecystectomy is recommended in Grade I patients, treatment options such as early cholecystectomy, late cholecystectomy after antibiotic therapy, and late cholecystectomy after cholecystostomy are left to the discretion of clinicians in Grade II high-risk and Grade III patients, depending on the clinical condition of the patient. Although there is no definite opinion about which treatment is superior today, the studies included patients in all three stages. In addition, most of the studies in the literature have been carried out retrospectively, and the number of prospective studies is very few. In this study, we will examine whether there is a significant difference in terms of difficult cholecystectomy, mortality and morbidity between early and late cholecystectomy in Grade II patients who are most difficult in the decision stage.

Koetsu Inoue et al. reported that there are fewer technical difficulties in cholecystectomies performed within the first 96 hours after admission with the diagnosis of acute cholecystitis (1).

In contrast, Yun-Xiao Lyu et al. showed that there is a significant difference between cholecystectomy performed at the first admission and cholecystectomy performed in the late period, only in terms of length of hospital stay (2). Ismael Mora-Guzmán et al. also reported in their study that there was no significant difference in complications between early and late cholecystectomy(3). Again, Vinoban Amirthalingam et al. It has been reported that early period cholecystectomy can be performed safely in Grade II and III patients (4). In all these studies, no clear distinction was made for early and late cholecystectomy, and both techniques were shown to be applicable.

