3. EXPECTED BENEFITS AND RISKS FROM THE RESEARCH

In this study, there is no expected risk since a different treatment method and medication will not be tried in previous similar studies. As a result of this study, if there is a difference between the research groups, new data will be obtained in terms of the approach to Grade II acute cholecystitis in the literature. Due to the limited number of prospective studies on this subject, the data to be obtained may change the treatment scheme to be applied in the future for the patient population in the research group and may benefit from reducing the complication rates.

4. TYPE, SCOPE, DESIGN AND THE DATA TO BE OBTAINED AFTER THE RESEARCH STATISTICAL TO BE USED IN THE EVALUATION METHODS

The research was planned as a prospective study. The study is single-centered and the patient group graded as Grade II according to the Tokyo 2018 guideline acute cholecystitis diagnostic criteria will be included in the study. Grade I and III patients, patients with accompanying choledocholithiasis, patients who are pregnant or likely to become pregnant, patients who cannot comply with the treatment due to their mental status and who cannot sign their own consent for treatment will not be included in the study. Patients classified as Grade II acute cholecystitis will be informed about the treatment options and possible complications after hospitalization. Patients will decide on the treatment method to be applied with their consent. The patients will be divided into two groups as those operated in the early period (first 7 days) and those operated in the late period (>6 weeks). The parameters to be compared were the rate of conversion from laparoscopic to open, bile duct injury and bile leakage rate, grade II-III complication rate in the Clavien Dindo complication scoring system, morbidity rate in the first 30 days postoperatively, and difficult cholecystectomy rate based on intraoperative imaging findings according to the Parkland scoring system. The research will be terminated when the number of 120 patients determined by the power analysis result is reached.

Chi-square and Student's t test will be used for the statistical evaluation of the results of the patients, respectively, for quantitative and continuous variables, and Mann-Whitney U test (two samples) or Kruskal-Wallis test (more than two samples) will be used for the analysis of abnormally distributed variables.

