5. THE NUMBER OF PATIENTS AND VOLUNTEERS TO BE INCLUDED IN THE RESEARCH QUALITY AND JUSTIFICATION OF SELECTION (AGE RANGE, GENDER ETC.).

The research population was determined as 120 patients as a result of the power analysis results. The number of volunteers will be 120, and the patient group graded as Grade II according to the Tokyo 2018 guideline acute cholecystitis diagnostic criteria will be included in the study, regardless of gender group over the age of 18.

6. PARAMETERS TO LOOK AT AND WHERE TO LOOK AT THE PARAMETERS AND BY WHOM

Parameters to be checked: Age, gender, comorbid diseases, previous abdominal operations, drug allergy, ASA score, Parkland score, length of hospital stay, duration of operation, amount of bleeding during the operation, type of operation, biliary tract complication, Clavien Dindo complication score, postoperative mortality and morbidity. The parameters will be checked and recorded by the principal investigator during the application and follow-up.

7. WHICH PARAMETERS TO BE USED IN THE RESEARCH ARE ROUTINE FOR THAT DISEASE GROUP AND WHICH ARE SPECIALLY REQUESTED FOR THE RESEARCH

Among the parameters and tests used in the research, there are no specific ones used for the research, and all of them are recorded and requested during the routine follow-up of the disease.

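### Groups are formed by patient choice, but no measure of acute severity within Grade II is listed at the index admission and the time of ASA scoring is not fixed

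*Combined protocol and SAP*

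**What the plan says.** Section 4 describes a single-centre prospective comparison of surgery in the first 7 days with surgery after more than 6 weeks. Allocation is not random: "Patients will decide on the treatment method to be applied with their consent". The planned tests (chi-square, t, Mann-Whitney, Kruskal-Wallis) are unadjusted, and no covariate is named.

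Entry is restricted by grade: "the patient group graded as Grade II according to the Tokyo 2018 guideline acute cholecystitis diagnostic criteria will be included in the study". Section 2 explains what the grade rests on: "patients were divided into three groups based on clinical findings, laboratory findings, and imaging findings".

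Section 6 gives the data to be collected. The list begins "Age, gender, comorbid diseases, previous abdominal operations, drug allergy, ASA score, Parkland score, length of hospital stay" and continues "duration of operation, amount of bleeding during the operation, type of operation, biliary tract complication, Clavien Dindo complication score, postoperative mortality and morbidity". On timing it says only this: "The parameters will be checked and recorded by the principal investigator during the application and follow-up". Section 7 adds that nothing is requested specially for the research, and that "all of them are recorded and requested during the routine follow-up of the disease".

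Section 4 bases the difficult-cholecystectomy rate on the Parkland score, taken from what is seen during the operation.

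**The concern.** When patients choose their own group, the groups can differ in how ill they were at the time of choosing. Restricting entry to Grade II removes differences between grades but leaves whatever variation exists within Grade II. The grade takes the same value for every patient, so it cannot show whether one group was the more severe.

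The findings that could show it must be looked at to establish eligibility, yet none of them is on the Section 6 list. A difference in difficult cholecystectomy or complications could then reflect who chose which timing, and the listed data could not tell the two explanations apart. Section 3 expects that the results may change how these patients are treated, so a difference needs to be interpretable.

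ASA is the listed item closest to overall condition at the time of choice, and its time point is open. If it were scored at different points of the illness in the two groups, a comparison of ASA would mix timing with true difference.

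**Working it through.** **1. Sorting the Section 6 list by its possible use as a baseline**

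- Fixed or slow to change, and recordable at presentation in both groups: age, gender, comorbid diseases, previous abdominal operations, drug allergy.
- Health status with no time point given: ASA.
- Fixed only at or after operation: Parkland, operating time, blood loss, type of operation, biliary complication, Clavien-Dindo score, mortality and morbidity. Length of stay also belongs here, as a consequence of care.
- Acute severity at the index admission: nothing. Symptom onset, laboratory values, imaging findings and the Grade II criteria met are all absent.

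Parkland fails as a substitute on two counts. In the late group it is scored more than 6 weeks after presentation, and it defines one of the outcomes, so adjusting for it would adjust for the result.

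**2. How large the distortion could be (illustration)**

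The plan gives no figure on this point. Its sample size of 120 is stated without inputs, and the point does not depend on it. All inputs below are assumptions.

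Let a binary severity marker within Grade II multiply complication risk by k. Let it be present in a share p1 of the early group and p0 of the late group, with no true effect of timing. The apparent risk ratio, early vs late, is

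(1 + (k − 1)p1) / (1 + (k − 1)p0)

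| Shares, early vs late | k = 2 | k = 3 |
|---|---|---|
| equal | 1.0 | 1.0 |
| 60% vs 40% | 1.6/1.4 = 1.14 | 2.2/1.8 = 1.22 |
| 70% vs 30% | 1.7/1.3 = 1.31 | 2.4/1.6 = 1.50 |

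If sicker patients choose late surgery, the ratios invert: 1.4/1.6 = 0.88, 1.8/2.2 = 0.82, 1.3/1.7 = 0.76 and 1.6/2.4 = 0.67.

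**3. The same idea on the scale of difficult cholecystectomy**

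Assume 60 patients per group, a two-sided 5% test and no true timing effect. Suppose difficult cholecystectomy occurs in 50% of more severe and 20% of less severe patients, and the more severe share is 60% early vs 30% late.

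- Early: 0.6 × 50% + 0.4 × 20% = 38%
- Late: 0.3 × 50% + 0.7 × 20% = 29%
- Spurious difference: 9 points. The chance of a significant result in that direction is about 18%, where 2.5% is intended.

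Other shares with the same rates: 50% vs 30% gives 6 points (about 10%), and 70% vs 30% gives 12 points (about 28%). If severity matters less (40% vs 30% difficult), the same three sets of shares give 2 to 4 points (about 4% to 7%).

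**4. What recording the marker would achieve**

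In this example the rates are 50% in both groups among the more severe and 20% in both among the less severe. The spurious difference disappears once patients are compared within levels of the marker. That comparison needs the marker on the data form.

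**The case against.** Several parts of the case on the other side stand.

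- A reader might infer that ASA is a pre-operative score and so falls after the wait in the late group. The documents do not say this. Section 6 speaks of recording at application as well as at follow-up, which allows ASA at presentation for everyone, and Section 7 says only that the items are routine. What can be shown is that the time is unspecified. Nor is any adjustment for ASA planned, so harm from adjusting for a mistimed score is only potential.
- A reader might infer that the study has no baseline taken at a common time. That is too strong. Five listed characteristics can be recorded at presentation in both groups and would change little during the wait. Comorbid disease is itself a health-status item.
- A reader might take Section 2 to say that timing in this study follows severity. The sentence in question says that options are "left to the discretion of clinicians in Grade II high-risk and Grade III patients, depending on the clinical condition of the patient". It describes what the guidelines leave open, whereas in this study the patient decides. Choice may still follow severity, but the documents state neither that it does nor in which direction.
- Acute severity is not wholly uncontrolled, because entry is limited to one grade.
- The grading findings probably exist in the charts, so their absence from Section 6 does not prove that they are lost for good.
- Every prevalence and risk factor in the illustration is assumed, and no imbalance at all is possible.

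None of this supplies a within-grade severity measure on the list. Retrieval from charts after the outcomes are known is possible, but it is less complete and less reliable than fields filled in before the choice is made.

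**Conclusion.** The point holds in this form: with groups formed by patient choice, Section 6 lists no measure of acute severity within Grade II at the index admission and does not fix when ASA is scored. A study run exactly as written could not examine or correct an imbalance in acute severity from its listed data.

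This conclusion rests on the text alone. The size of any bias does not: on the assumed inputs the apparent risk ratio with no true effect runs from 0.67 through 1.0 to 1.50, and the documents give no basis for choosing a value or a direction within that range. It would be wrong to conclude that the comparison is biased by a known amount, that ASA is taken after recovery in late patients, or that no common baseline exists. The change is a worthwhile, cheap improvement, provided that the recorded values are then used in the analysis.

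**What to change.** **Section 6.** Add the date of symptom onset, the Grade II criteria met, and the laboratory and imaging findings used for grading. State that these are recorded for every patient at the index admission, before the choice of group. State that ASA is scored at that same time. Keep any later pre-operative ASA as a separate field and do not use it as a baseline covariate. A high-risk flag within Grade II should not be added unless it is first defined, since Section 2 uses the term without a definition.

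**Section 4.** Add a between-group comparison of the index values. Add an analysis of difficult cholecystectomy adjusted for a small set of them named in advance (for example age, ASA and one severity measure), reported beside the unadjusted tests. New fields without this step would leave the planned comparison unchanged.

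**Cost.** A few data fields taken from findings already needed to establish eligibility, and one ASA score at admission. No new tests and no change to patient care. The number of covariates must stay small: at the illustrative rates above, 60 × 0.38 + 60 × 0.29 gives about 40 difficult operations among 120 patients. Adjustment handles only what is measured, so unmeasured reasons for the patient's choice would remain a limitation to report.

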8. PROJECTED WORKING TIME, START AND END DATES

The duration of the study was planned as 18 months, and the study date range was determined as 14.12.2019-14.06.2021.

9. WITHDRAWAL AND TERMINATION CRITERIA

When patients want to leave the study, they can leave the study provided that they inform the principal investigator. The research doctor, who is also the coordinator of the study, may remove the patient from the study without informing the patient due to my negligence in fulfilling the requirements of the study program or in order to improve the quality of the medical care I am receiving.

The research will be terminated if the determined population (even earlier than the determined date) is reached.

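### Section 9 allows discretionary, undisclosed removal of enrolled patients, and with groups defined by the operation performed, failures of the chosen strategy can leave the comparison

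*Combined protocol and SAP*

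**What the plan says.** **Removal (Section 9).** The person with the power to remove is described as "The research doctor, who is also the coordinator of the study". This person "may remove the patient from the study without informing the patient due to my negligence in fulfilling the requirements of the study program", with a second ground added: "in order to improve the quality of the medical care I am receiving". The section gives no criteria, time limit, independent review or duty to record the reason. A patient who wants to leave must tell the principal investigator; a patient who is removed need not be told.

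**Treatment and groups (Section 4).** "Patients will decide on the treatment method to be applied with their consent". Then: "The patients will be divided into two groups as those operated in the early period (first 7 days) and those operated in the late period" (more than 6 weeks). So treatment is chosen openly, but group membership follows the timing of the operation performed.

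**Outcomes (Sections 4 and 6).** The comparison covers conversion to open surgery, bile duct injury and leak, Clavien-Dindo grade II-III complications, the Parkland-based rate of difficult cholecystectomy, and "morbidity rate in the first 30 days postoperatively". On recording, Section 6 says: "The parameters will be checked and recorded by the principal investigator during the application and follow-up".

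**Analysis (Section 4).** Only two-group (or multi-group) tests are named. No analysis population, rule for missing data or rule for removed patients is given. The study ends at 120 patients, and the plan does not say whether removed patients count towards that number or are replaced.

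**The concern.** Patients who do not follow the programme, or who need different care, are unlikely to have the same prognosis as the rest. If they can be taken out after enrolment by someone who knows which treatment they chose, and nothing retains their data, the analysed patients are a selected subset.

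The study asks whether early or late surgery is better in Grade II cholecystitis. Deterioration during the wait, or never reaching the delayed operation, is part of what the late strategy costs. If those patients are absent, the comparison describes only those in whom each strategy worked out as planned, and the report may not show how many were lost or why.

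**Working it through.** No figure in the plan can be reproduced here. The 120 is attributed to a power analysis, but its rates, effect size, power, significance level and allocation ratio are not given. The check is therefore a tracing of patients through the rules, followed by a test of what the timing figures can support.

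**Step 1. Where each patient ends up under Sections 4 and 9 as written.**

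| Course after enrolment | Analysed group |
|---|---|
| Chose early, operated within 7 days | Early |
| Chose late, operated after more than 6 weeks | Late |
| Chose late, operated within 7 days | Early, despite the choice |
| Chose late, operated between day 7 and week 6 | Neither |
| Chose late, never operated on | Neither |
| Chose early, not operated on by day 7, operated before week 6 or never | Neither |
| Removed under Section 9 before surgery | No provision to follow or analyse |
| Removed under Section 9 after surgery | No provision to follow or analyse |

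The rows for patients who fall in neither group or change group arise from Section 4 alone. Section 9 adds a discretionary route, which also reaches patients already operated on.

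**Step 2. Does the wait point to more losses from the late group?**

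Inputs: 7 days and 6 weeks (Section 4); 30 days after surgery (Section 4, stated for morbidity).

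- Time to surgery: early at most 7 days; late more than 6 × 7 = 42 days.
- Time to 30 days after surgery: early at most 7 + 30 = 37 days; late at least 42 + 30 = 72 days.
- Late share of total time, assuming equal group sizes and the same constant removal rate per day: 42/(7 + 42) = 86% to surgery; 72/(37 + 72) = 66% to 30 days after it.

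The assumptions are not in the plan. It also does not define when the 7 days start or when the removal rule stops applying.

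**Step 3. What the extra time can explain.**

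The gap is 72 − 37 = 35 days, and 42 − 7 = 35 days of it falls before surgery. After surgery both groups have the same 30 days. The outcomes listed in Section 4 arise at or after surgery. The longer wait can therefore lead to loss of late patients who are doing badly before any listed outcome exists. It gives no reason to expect more removals of late patients who have already had a recorded postoperative event.

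**Step 4. Size.**

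A bias in percentage points needs the event rate, the number in each group, the number removed and the event risk among those removed. The plan gives none of the four, and group sizes depend on patients' choices. No estimate follows.

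**The case against.** **The wording is consent-form language.** The first-person phrases suggest pasted text, and nothing shows an intention to exclude selectively. That is fair as to intent. It is still the only investigator-initiated removal rule in the plan, and following it as written permits the exclusions.

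**The plan does not say that removed patients' data are discarded.** True; it is silent. But no analysis population or retention rule exists elsewhere to fill the gap.

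**The main loss comes from Section 4, not Section 9.** This stands. A patient who misses the late operation is outside both groups without anyone using Section 9, so rewording Section 9 alone would not be enough.

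**Stronger readings that a reader might infer:**

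- *That removals will fall mostly in the late group.* The plan does not state this. It is plausible from the wait, but the shares in the working rest on an assumed equal removal rate and equal groups.
- *That the bias can be given a size by deleting some late events from an assumed 60 per group.* Those deletions would have to follow surgery, where the two groups have equal follow-up, and would have to spare early patients and event-free patients. Even then, a false significant result needs heavy removal. With 20% events in both groups, 9 of the 12 late events must go (12/60 v 3/51, p = 0.030, chi-square without continuity correction). With 30%, it is 12 of 18 (18/60 v 6/48, p = 0.030). With 40%, removing 12 of 24 does not suffice (24/60 v 12/48, p = 0.10). All of these inputs are assumed.
- *That the same person records outcomes and removes patients.* Section 6 names the principal investigator as recorder; Section 9 names the research doctor and coordinator as remover. The plan does not say whether they are one person.
- *That removed patients lose their follow-up care.* Section 7 says all parameters belong to routine follow-up, so removal does not by itself end care.

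**Conclusion.** The point holds in this form: Section 9 permits discretionary removal after enrolment, without telling the patient, on grounds that can be related to prognosis, by a doctor for whom no blinding is described. No rule retains removed patients. Combined with the definition of groups in Section 4, this lets failures of the chosen strategy leave the comparison. This is more than missing detail, because carrying out the plan as written allows it.

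The likely direction is towards making late surgery look better, if those lost are mainly patients who deteriorate or miss the delayed operation. That direction is an inference from the wait of more than 6 weeks against at most 7 days. The size cannot be derived from the plan. The conclusion does not depend on the assumed removal rates or group sizes; it rests on the text of Sections 4 and 9 and on the absence of an analysis population. The change should be made.

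**What to change.** **Section 9.**
- State that non-compliance or a change in care does not remove a patient from the study.
- State that data collection stops only when the patient withdraws consent, and that data up to that point are kept.
- Delete the permission to remove patients without telling them. This is a consent matter and does not in itself reduce bias.
- Report every withdrawal by group, with its reason.

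**Section 4.**
- Define the main comparison by the treatment chosen at enrolment, with all enrolled patients included for outcomes that can be assessed in everyone, such as morbidity and mortality. The present morbidity outcome is counted from surgery, so a version counted from enrolment over a stated period is needed for patients never operated on.
- Analyse operative outcomes (Parkland score, conversion) among operated patients, and label them as such.
- Report, by chosen group, how many were not operated on and how many were operated on outside either window.
- State whether the 120 counts all enrolled patients.

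**Cost.** Two sections are reworded, with a small amount of extra tracking and analysis. Section 7 says all parameters are already routine, so little new data collection is needed. Operative outcomes remain undefined for patients never operated on, and that comparison stays selected. Analysis by chosen treatment also does not remove differences between patients who choose early and those who choose late.
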